Because this is part of early-stage intervention development activities (Stage 1), we have designed a clinical trial to pilot-test feasibility as well as efficacy of the redeveloped TLC intervention. We propose to use a waitlist control cohort design, using a fully powered sample to provide the most rigorous analysis possible. The waitlist design allows all participants to receive the intervention. As shown here in the figure, participants will be randomized to one of two sequences. After baseline data collection and an initial orientation/control period for the first 4 weeks, Group A will have 8 weeks of TLC intervention, then 8 weeks of follow-up. Group B will have 8 weeks of waitlist control, and then TLC intervention for 8 weeks, beginning at week 12. We will use ecological momentary assessment (EMA) during the entire 20-week study period to capture daily time-use trends for any respite periods received (n=140 daily reports, max). EMA aims to minimize recall bias and maximize ecological validity. Primary outcomes data will be collected via electronically administered surveys at baseline (T0) and every 4 weeks thereafter (T4, T8, T12, T16, T20), for a total of 6 assessments. This randomized, prospective, and longitudinal design

allows each participant to serve as its own control and offers opportunities to assess both within- and between-group differences over time (Group A vs. B).

Measures

The primary outcome is wellbeing, measured with two standardized scales indicating “caregiver burden” and “anxiety.” The mechanism driving the intervention effect is theorized to be related to respite time-use and time-use satisfaction. This construct is measured with “experienced” and “evaluative” time-use measures.

Analysis

The analysis to test for efficacy will specifically look at treatment x time interaction that combines both vertical (between individuals at given timepoints) as well as horizontal (evolution within individual over time) comparisons. We will utilize a multilevel model that consists of level 1 (within person) and level 2 (between person). Thus, the overall composite two level Multi-Level Mixed effects Model (MLM) is defined as follows with the first set of brackets representing fixed effects and second set random effects:

$$Y_{ij} = [\beta_0 + \beta_1 T_j + \beta_2 X_{ij}] + [\zeta_{0i} + \zeta_{1i} T_{ij} + \epsilon_{ij}] \quad [\text{equation 1}]$$

[figure not shown]

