where Y_{ij} is the outcome measure (Caregiver Burden and Anxiety) for participant (i) at time (j) where j is an indicator for time (baseline, 4 weeks, 8 weeks, 12 weeks, 16 weeks and 20 weeks). β_0 is the population mean level of the outcome measure prior to the TLC intervention, β_1 fixed effect for time independent of intervention, X_{ij} is the intervention status (pre-TLC or Post-TLC/Follow-up) at timepoint j, and β_2 is the intervention treatment effect. Random effects include individual-level intercept (ζ_{0i}), individual-level slope of change over time ($\zeta_{1i} T_{ij}$), and ϵ_{ij} for residual error of each outcome measure. Our hypotheses for Aim 2 are summarized here:

Over time, we expect intervention engagement to produce more positive wellbeing, with time satisfaction as the mechanism through which TLC achieves its effect.

- H1:** Burden & anxiety will be lower among the treatment group compared to those in control/waitlist condition (direct effect)
- H2:** Time-use satisfaction will be higher among the treatment group compared to those in control/waitlist (direct effect)
- H3:** Higher time-use satisfaction will be associated with lower burden & anxiety (direct effect)
- H4:** Higher time-use satisfaction will mediate the effect of the intervention on burden and anxiety (direct & indirect effect)

H1: Burden & anxiety will be lower among the treatment group compared to those in control/waitlist condition (direct effect)

Figure 2: Anticipated results for Wellbeing with TLC

Our primary outcome will test the hypothesis that there will be significant change in “caregiver burden” or “anxiety” immediately post intervention. Figure 2 shows the anticipated results with no change during the run-in period, increase in wellbeing in Group A during the intervention but not WLC. Group B then shows increased wellbeing during TLC, with Group A maintaining or slight decrease in “caregiver burden” or “anxiety” over time. With the planned 120 participants (60 per group), we will be able to detect small to medium effect sizes on the two outcomes with greater than 90% Power (see below). Intent-to-treat analyses (ITT) will be performed on non-completers using a terminal score for both “caregiver burden” and “anxiety” scores.

H2: Time-use satisfaction will be higher among the treatment group compared to those in control/waitlist (direct effect)

[figure not shown]

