Time-use satisfaction data will be collected daily using EMA, of short questions. First, did you have respite today? Then, if yes, how satisfied are you with your respite time-use? (1-

5) Did the respite time make you feel more positive/negative about your role as a caregiver? (1-5). These two items measure “experienced” and “evaluative” time-use measures, respectively, which have been theorized to be associated with the wellbeing outcomes (anxiety & caregiver burden). Aggregated averages of these two measures will be computed for specific time-periods (i.e., across the four-week interval spanning the primary data collection timepoints). The same MLM will test significance of time x intervention interaction on mean Time-use satisfaction following TLC intervention compared to WLC.

H3: Higher time-use satisfaction will be associated with lower burden & anxiety (direct effect)

Using the same MLM framework, we will examine if aggregate Time-Use Satisfaction (predictor) is associated with lower “caregiver burden” and “anxiety.” As an exploratory aim we will examine Time (β_1) immediately post intervention through follow up to determine maintenance, attenuation, or no change in Group A outcomes after TLC for wellbeing (anxiety & caregiver burden) and time-use satisfaction (experienced & evaluative time-use).

Figure 3: Time-use mediates TLC impact on Well Being

H4: Higher time-use satisfaction will mediate the effect of the intervention on burden and anxiety (direct & indirect effects)

Figure 3 displays our overall mediation model, whereby TLC intervention improves wellbeing by increasing Respite Time-Use Satisfaction. We hypothesize that “satisfaction with respite time-use” is the factor that links respite use with wellbeing outcomes such that TLC intervention leads to improvements in respite quality that in turn produces better outcomes over time.

Mediation analysis will be conducted as previously outlined for cross-sectional as longitudinal models.^{149, 138, 139} In its simplest form, mediation is represented by three linear equations

$$\text{Mediator (Time-Use)} = i1 + aX + e1 \quad (2)$$

$$Y (\text{Wellbeing}) = i2 + cX + e2 \quad [\text{without mediator}] \quad (3)$$

$$Y (\text{Wellbeing}) = i3 + c'X + bM + e2 \quad [\text{with mediator}] \quad (4)$$

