When substituting the Mediator M in equation 3 the indirect pathway by which the TLC intervention impacts wellbeing through time-use is represented by the product of coefficients $a \cdot b$. If significant, then mediation is present. If the direct pathway c in equation 3 becomes non-significant in equation 4 (c') when conditioning on the indirect pathway, then M is said to fully mediate the relationship between TLC and wellbeing. Importantly, in the models we will control for individual values of the wellbeing outcomes obtained before the start of the TLC intervention. The indirect pathway will be tested using the Sobel test that divides product-of-coefficients $a \cdot b$ by the first-order delta-method standard error of the indirect effect. This value is compared against a standard normal distribution to test for significance.¹⁴⁸ We will also consider additional statistical mediation tests that account for non-normality of the product of coefficients and/or bootstrapping methods for more accurate estimates.¹²¹

Although not stated as distinct hypotheses, we will conduct additional exploratory analyses to further explain for whom and how the intervention achieves its effect. These analyses will be guided by the following questions: Do variations in the receipt of the intervention modify these relationships? For example, do participants that report higher intervention feasibility (i.e., higher satisfaction and usability of the tool) or higher dosage (i.e., they accessed more of the intervention's features) show stronger treatment effects? This will be assessed by replacing the dichotomous intervention variable X (TLC vs. WLC) in equation 1 with measures indicating dosage or perceived feasibility. Similarly, we will explore whether individual characteristics or circumstances modify the relationship between intervention, time-use satisfaction, and wellbeing over time. Here, we will use biologic variables of gender and age as well as measures that capture changes in the context of the caregiving relationship as both control variables and interaction. Finally, we will explore whether treatment effects maintain, attenuate, or no-change once the intervention period ends. This will be assessed using a repeated-measures design using Group A's data from immediately post-intervention through the 8-week follow-up period.

Power and Sample Size

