We assume clinically relevant small to medium effect sizes in the main outcomes of interest corresponding to 4-6.5 mean change on the total "caregiver burden" outcome and 1.0-1.4 mean change on the "anxiety" outcome. Power and sensitivity analysis were computed in GPower using RMANOVA finding a total sample of 116 would be sufficient to achieve

power of greater than 90% to detect these effect sizes. Therefore, we will aim to have a final sample size of 120 (60 in each sequence) with a 25% over-recruitment to account for study attrition providing a total sample size of 150.

Sample size and sensitivity analyses for mediation analyses are based on empirical estimates conducted by Fritz and MacKinnon (2007).¹²¹ Assuming medium effects for each of the two parts of the indirect pathways (i.e. TLC->Time-use and Time-use->Wellbeing) in Figure 3, a sample size of 75-120 will provide greater than 80% Power (Sobel148 medium-medium effects) at $p=0.05$.

Missing Data

We will explore missing data patterns in SPSS using the Missing Value Analysis tool. We will specify the pattern fixed effects and interactions utilizing Little's test for Missing Completely at Random. In keeping with an intent-to-treat standard and assuming maximum likelihood estimation, we will use all available data for analyses. It is not necessary to eliminate observations from participants who subsequently drop out, nor is it necessary to impute individual observations. Both practices can bias estimation and distort variability. The maximum likelihood estimates given the observed data points are the values most likely to have generated the complete ensemble of observed sample data under the assumed model. Systematic missingness (as determined by missing data patterns) may be included in our mixed effects model. Potentially non-ignorable missing data will be investigated using multiple imputation sensitivity analyses under a diverse set of covariate predictors. To minimize loss of scale scores due to missing items in a computed scale, we will prorate the respondent's score based on available items. If a respondent is missing more than 30% of the items in a computed score for the primary outcome variables, we will code the scale score as missing.

Note: feasibility is another primary outcome of the pilot test. Feasibility-related analyses are discussed at the end of this document, since the focus on feasibility and the analytic strategies to measure feasibility are shared across Aims 1, 2, and 3.

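### The H4 plan would report full mediation from a non-significant direct effect, which does not show that the direct effect is absent

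*Combined protocol and SAP*

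**What the plan says.** The H4 text introduces mediation through a simple set of models: "In its simplest form, mediation is represented by three linear equations". Equation 2 gives a (intervention to time-use satisfaction), equation 3 gives c (total effect on wellbeing), and equation 4 gives c' (direct effect) and b.

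Two decisions follow. Mediation is declared present if a·b is significant by the Sobel test. A second sentence then separates full from partial mediation: "If the direct pathway c in equation 3 becomes non-significant in equation 4" once the mediator is in the model, "then M is said to fully mediate the relationship between TLC and wellbeing".

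The same paragraph adds that "in the models we will control for individual values of the wellbeing outcomes obtained before the start of the TLC intervention". It also allows bootstrap methods, or methods that allow for non-normality of the product of coefficients.

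Power and Sample Size claims, for 116 participants, "power of greater than 90% to detect these effect sizes" on the main outcomes, and more than 80% power for mediation with medium effects on the two parts of the indirect path. It gives no power for c'.

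**The concern.** A non-significant c' has two possible explanations: the direct effect is close to zero, or the trial cannot estimate it precisely enough to tell. The rule treats both as the first. Once a·b and c are significant, a wider interval around c' makes the full-mediation label more likely.

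What is at stake is the reported mechanism. The Aim 2 text introduces its hypotheses "with time satisfaction as the mechanism through which TLC achieves its effect", and the H4 text says that time-use satisfaction "is the factor that links respite use with wellbeing outcomes". A false full-mediation statement would tell those who develop the intervention further that it works only through time-use satisfaction, when a substantial part of its effect may run by another route.

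**Working it through.** **1. What the rule needs.** Three conditions apply: (i) a·b is significant; (ii) c is significant in equation 3, which is implied because c has to *become* non-significant; (iii) c' is not significant in equation 4. Conditions (i) and (ii) support a total effect and some mediation. Only (iii) distinguishes full from partial.

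**2. Is there another criterion for full?** None appears in the Analysis, H4, Power and Sample Size or Missing Data text: no margin, equivalence test, interval, proportion-mediated threshold or power for c'. The bootstrap option is justified by the product a·b. Control for pre-intervention wellbeing can shrink the standard error of c', but condition (iii) stays as it is.

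**3. The plan's own figures.** 120 × 1.25 = 150 reproduces. The mediation power cannot be verified, because medium has no number and sidedness is not stated. With standardised paths of 0.39 (assumed), simulated Sobel power is 0.67 at 75, 0.80 at 90 and 0.94 at 120. None of these figures concerns c'.

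**4. What a zero estimate of c' could exclude.** Inputs from the plan: 116 participants for the power calculation, 120 planned, and 4 burden points (low end of the assumed 4–6.5). Assumptions: the power statement applies to c; two-sided 0.05; power of 90% (the floor of the claim) or 99%; r = SE(c')/SE(c) of 0.85–1.07 (90%) or 0.72–1.06 (99%), taken from the simulation in step 6.

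Noncentrality of c at 120 = (1.96 + z_power) × √(120/116):
- 90%: (1.96 + 1.282) × 1.017 = 3.30
- 99%: (1.96 + 2.326) × 1.017 = 4.36

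95% half-width for c' as a share of c = 1.96 × r / noncentrality:

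| Power for c | r | Share of c | Burden points (× 4) |
|---|---|---|---|
| 90% | 0.85 to 1.07 | 51% to 64% | 2.0 to 2.5 |
| 99% | 0.72 to 1.06 | 32% to 48% | 1.3 to 1.9 |

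**5. Power for c' if half of c is direct.** Power ≈ Φ(0.5 × noncentrality / r − 1.96).
- 90%: 0.5 × 3.30/1.07 = 1.54 gives 34%; 0.5 × 3.30/0.85 = 1.94 gives 49%.
- 99%: 0.5 × 4.36/1.06 = 2.06 gives 54%; 0.5 × 4.36/0.72 = 3.03 gives 86%.

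**6. How often the label would be wrong.** The longitudinal simulation used 120 participants and the planned outcome schedule ("for a total of 6 assessments"). Intervention status switched on from T8 (Group A) and T16 (Group B). It had random intercept and slope, intraclass correlation 0.5–0.7, a of 0.3–0.8 SD, c set for 90% or 99% power at 116, c' = 0.5c, and no dropout. Among trials with significant a·b and c, roughly 40–65% (90% power) or 5–50% (99% power) were labelled full although half the effect was direct. In the planned design the mediator has no T0 value, because it is averaged from daily reports over four-week intervals. Runs with five mediator values gave 46–63% and 9–50%, inside those ranges.

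A single-level version of equations 2–4 (120 participants, b = 0.39, c' = 0.3 SD, all assumed) shows the effect of baseline control. With a = 0.78 the direct share is 0.30/(0.30 + 0.78 × 0.39) = 50%, and the label is given in 64%. With a = 0.5 the share is 61%, and the label is given in 58%. With a baseline–outcome correlation of 0.5 the rates are 49–58%, and with 0.7 they are 38–43%. Other assumed paths and scalings, with 60% direct and correlation 0.7, gave 0.4–47%.

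**The case against.** The strongest reply is that this sentence repeats a textbook convention, attached to mediation in its simplest form, in a Stage 1 pilot that is meant to explore efficacy and mechanism. The longitudinal method is left to cited references. That limits the weight of the point. But the sentence is the plan's only stated reading of c', and it carries no caveat.

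A reader might infer that the plan predicts full mediation, so that the rule hands back its expected answer. The documents do not support this. H4 says that time-use satisfaction will mediate and names both direct and indirect effects. The phrases about the mechanism and the factor are informal.

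A reader might also infer that a non-significant c' alone triggers the label, or that an imprecise trial would simply return it. Neither holds. Both a·b and c must be significant first, and general imprecision makes those two conditions harder to meet.

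Finally, the simulated rates depend heavily on assumptions. The documents give no direct share, path sizes or variance components, and the rate can be near zero when the direct share is larger, the paths are strong and baseline is highly predictive. This stands, so the rates are only rough illustrations. The logical point does not depend on them.

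**Conclusion.** The point holds for the full-mediation label and for nothing beyond it. Where a·b and c are significant, the plan would read failure to reject c' = 0 as evidence that no direct effect remains, and nothing else in the plan supports that reading. Baseline control improves precision but does not make the inference valid.

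On the size, even an estimate of exactly zero would leave a direct effect of about half to two-thirds of c unexcluded if c is powered at 90%, and about a third to a half at 99%. This assumes that the power statement concerns c at the low end of the burden range, two-sided 0.05, and it uses simulated standard-error ratios.

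The a·b test of H4, the sample size, the feasibility benchmarks and data collection are unaffected. The correction should be made, but it concerns a stated conclusion about mechanism, not the efficacy analysis.

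**What to change.** Delete the full-mediation sentence from the H4 text. In its place, state that a·b and c' will each be reported with a 95% confidence interval from the planned mediation model, and that a non-significant c' will not be read as full mediation. The Sobel test of a·b can stay as it is.

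The cost is one sentence removed and one added. Equations 2 and 4 already estimate a, b and c', so sample size and data collection do not change. The plan gives up only the full-mediation label.

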Upon consent, participants will be randomly assigned to Group #1 or Group #2. The study design is akin to a waitlist control design, with group #1 (treatment group) receiving 8 weeks of intervention followed by 8 weeks of continued use of TLC intervention tools, and group #2 (waitlist group) doing respite as usual for 8 weeks, followed by 8 weeks of more intensive coaching from the TLC intervention. Both group #1 and #2 will fill out daily/weekly reviews of their respite use throughout the calendar functions of the TLC intervention tools during the 16-week intervention period, as well as monthly questionnaires at baseline/enrollment, week 4, week 8, week 12, week 16, and week 20.

Note: when we created the online, self-administered version of the TLC intervention, we merged all data collection instruments with intervention prompts into a single online delivery package, so both group #1 and group #2 receive access to the TLC study tools from day 1 and end their access at the end of week 20. This has altered the traditional "waitlist" (i.e., no contact) condition associated with group #2. Both group #1 and group #2 receive the same instructions and orientation to the study on day 1. The groups differ only in the amount and type of "virtual coaching" (instructions and prompts from the TLC website) they receive at week 1 and week 9. Group #1 receives more intensive coaching at week 1, with an encouragement to continue doing it on their own at week 9. Group #2 receives less intensive coaching at week 1, with a more intensive coaching instructions presented to them at week 9.

Self-administered questionnaires and daily ecological momentary assessments (EMAs). Participants in both conditions will complete self-administered questionnaires at baseline, and then every 4 weeks thereafter (for a total of 6 questionnaires, spread across 20 weeks). All questionnaires will be distributed electronically via email. Responses will automatically be recorded in a secure REDCap data base.

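### H4 adjusts for pre-TLC wellbeing but not for run-in time-use satisfaction, which the Study Design schedule already collects in both groups

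*Combined protocol and SAP*

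**What the plan says.** The H4 section gives three linear equations: the mediator on intervention (equation 2), wellbeing on intervention (equation 3), and wellbeing on intervention and mediator (equation 4). The indirect effect a·b is tested by Sobel, with bootstrap or other tests to be considered. On covariates it says "in the models we will control for individual values of the wellbeing outcomes obtained before the start of the TLC intervention". No earlier mediator value is named. Gender, age and caregiving context enter only in exploratory analyses.

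The Study Design section places TLC later than enrolment: "After baseline data collection and an initial orientation/control period for the first 4 weeks", Group A has 8 weeks of intervention and Group B 8 weeks of waitlist. It adds: "We will use ecological momentary assessment (EMA) during the entire 20-week study period". Under H2 the daily ratings are averaged "across the four-week interval spanning the primary data collection timepoints". On that schedule one average, weeks 1–4, precedes TLC in both groups.

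The Procedures section describes a different start: "Group #1 receives more intensive coaching at week 1, with an encouragement to continue doing it on their own at week 9". There, weeks 1–4 already contain intensive coaching in Group #1.

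**The concern.** The plan treats pre-TLC adjustment as important but applies it only to the outcome.

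- **Path a (TLC to satisfaction)** is a randomised comparison. Leaving out a baseline of the same measure causes no bias, but it loses precision to the extent that run-in satisfaction predicts later satisfaction.
- **Path b (satisfaction to burden or anxiety)** is observational, because caregivers are not randomised to satisfaction. If generally satisfied caregivers are also generally less burdened, path b picks up that association. Pre-TLC wellbeing removes only part of it.

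At stake are the power of H4 when mediation is real and, under correlated traits, its error rate when it is not.

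**Working it through.** **Inputs from the documents.** Final n=120, 60 per sequence; Sobel test; level 0.05 (taken as two-sided); more than 80% power claimed for n=75–120 (Power and Sample Size). The effect size is given only in words: "Assuming medium effects for each of the two parts of the indirect pathways". **Assumed, because the documents are silent:** run-in-to-later correlation of satisfaction (rho), stability of wellbeing, correlation of the stable traits, and a numerical value for a medium effect.

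**1. The plan's own power figure.** Simulating equations 2–4 without covariates at n=120 gives Sobel power of 94% if both paths are 0.39 standardised, 70% if both are r=0.3, and 66% if the intervention is binary with d=0.5 and b=0.39. At n=75 with 0.39/0.39 it is 66%, and it reaches 80% at about n=90. The claim at n=120 is thus met on one of three readings, so H4 may have little power to spare.

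**2. Path a.** With a mediator SD of 1, SE = 2/√120 × √(1−rho²), and power ≈ Φ(0.5/SE − 1.96).

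| rho | SE | Power, 60 per arm |
|---|---|---|
| not adjusted | 0.183 | Φ(0.779) = 78.2% |
| 0.3 | 0.174 | 81.9% |
| 0.4 | 0.167 | 84.8% |
| 0.5 | 0.158 | 88.5% |
| 0.6 | 0.146 | 92.8% |
| 0.7 | 0.130 | 97.0% |

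Simulation with pre-TLC wellbeing in both models agrees. The SE goes from 0.183 to 0.168 at rho 0.4 and 0.131 at rho 0.7, that is 0.015/0.183 = 8% and 0.052/0.183 = 28%. Power goes from about 77% to 83–97%. Where pre-TLC wellbeing itself predicts satisfaction, the unadjusted SE is already smaller (down to 0.159) and the proportional gain is less.

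**3. Sobel power, true b = −0.3.** Power rose in every scenario run, but by very different amounts.

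- With uncorrelated traits, and pre-TLC wellbeing not itself affected by run-in satisfaction, it goes from about 61% to 63–64%.
- If pre-TLC wellbeing already reflects run-in satisfaction, the range is 28–76% under the plan and 58–89% with the run-in mean. The largest gain comes from adjusting for pre-TLC wellbeing alone, which pulls b toward zero: with uncorrelated traits, b is estimated at −0.16 to −0.26 under the plan and about −0.30 with the run-in mean.

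**4. Path b and false mediation, true b = 0.**

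- Trait correlation −0.3 to −0.5, rho 0.3–0.7: estimated b is −0.12 to −0.35 with no covariate, −0.04 to −0.16 under the plan, and −0.03 to −0.09 with the run-in mean. Sobel rejections are 2.7–19.9% under the plan and 2.2–6.3% with the run-in mean.
- Trait correlation −0.4 to −0.6, a=0.5, wellbeing stability 0.6, one pre-TLC wellbeing value: about 6–31% under the plan and 4–10% with the run-in mean.
- Uncorrelated traits: 0.3–2.1% under the plan and 1.4–2.9% with the run-in mean. There is no inflation to remove.
- Using both T0 and T4 wellbeing, without run-in satisfaction, roughly halves the rate (for example 41.8% to 19.8% in the most severe case at a=0.6).

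All of these runs assume that every caregiver has a run-in mean.

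**The case against.** **The equations are schematic.** The plan introduces them as the simplest form and refers to longitudinal mediation methods, which can carry earlier mediator values. That makes this an under-specification, not a decision to exclude. The point stands all the same: the plan names wellbeing explicitly, and nothing supplies the mediator baseline.

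**The baseline may not exist.** The Procedures section describes the merged online package, with both groups using the tools from day 1 and Group #1 coached intensively from week 1. On that schedule the weeks 1–4 mean is post-treatment in Group #1. This objection stands in full and makes the recommendation conditional.

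**Pre-TLC wellbeing already does much of the work.** In the second-listed b = 0 comparison in the plan's favour, it removes about half or more of the path-b confounding, and the wording can be read as including both T0 and T4. This also stands.

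**Stronger readings to avoid.** A reader might infer that H4 as planned will usually declare false mediation, since rates above 40% can be produced. Those need a=0.6, strongly correlated traits and a single wellbeing value; at a=0.5 the same worst case is about 31%, and with uncorrelated traits about 1%. A reader might also infer that the run-in mean would remove confounding from path b. It does not: one four-week average is a noisy measure of a trait. Nor does it always move b closer to the truth. With a true b of −0.3, trait correlation −0.5 and both stabilities 0.7, the plan's estimate is −0.303 and the adjusted one −0.371, because errors under the plan partly cancel.

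**Conclusion.** The omission is real under the Study Design schedule, and its consequence is modest. The path-a gain is the firmest part, since it follows from a closed form for any positive correlation between run-in and later satisfaction: an SE about 8–28% smaller at rho 0.4–0.7. The gain in Sobel power has a consistent direction but an uncertain size. The reduction in false mediation depends on correlated stable traits, and using T0 and T4 wellbeing achieves about half of it. No correlation is given in the documents, so every size is an illustration.

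The documents do not support extending this to the main results. H1 does not involve the mediator, and H2's mixed model already uses the run-in interval as a repeated measure. The point concerns a mechanism analysis in a pilot, and it applies only if a pre-coaching period is confirmed.

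**What to change.** 1. Reconcile the Procedures and Study Design sections on whether a 4-week period precedes coaching.
2. If it does, state under H4 that equations 2, 3 and 4 adjust for each caregiver's run-in (weeks 1–4) mean of the same satisfaction item, and for wellbeing at T0 and T4. Fix these time points for both groups; otherwise the pre-TLC value in Group B could be read as week 12, after the parallel comparison.
3. Keep caregivers with no rated respite day in weeks 1–4 by a joint likelihood model or multiple imputation. A missing indicator would be acceptable for the randomised path a, but in the observational path b it leaves confounding uncorrected among those caregivers.
4. If coaching starts in week 1, state that weeks 1–4 are not used as a baseline covariate.

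The cost is a few sentences in the analysis plan and no new data collection. The one downside is the need for a missing-baseline rule, because eligibility includes caregivers who are only interested in using respite.

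### H4 is tested with the Sobel z against a normal reference, a conservative choice costing about 3 to 21 points of power at n=120, depending on path sizes the plan does not state

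*Combined protocol and SAP*

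**What the plan says.** The H4 text under Statistical Design & Power - Aim 2 commits to one test: "The indirect pathway will be tested using the Sobel test that divides product-of-coefficients" by the first-order delta-method standard error. It continues: "This value is compared against a standard normal distribution to test for significance". The next sentence acknowledges the weakness: "We will also consider additional statistical mediation tests that account for non-normality of the product of coefficients and/or bootstrapping methods for more accurate estimates". No alternative is selected, and nothing says what happens if it disagrees with Sobel.

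Power and Sample Size rests the mediation power on the same test. The premise is "Assuming medium effects for each of the two parts of the indirect pathways", and the result is that "a sample size of 75-120 will provide greater than 80% Power (Sobel148 medium-medium effects) at $p=0.05". No numeric path size is given, and the test is not said to be one- or two-sided. The planned analysed size is a "final sample size of 120 (60 in each sequence) with a 25% over-recruitment", giving 150 recruited.

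On the model, the H4 text states: "In its simplest form, mediation is represented by three linear equations". It also refers to longitudinal models and to adjustment for wellbeing measured before the intervention starts.

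**The concern.** The product of two estimated coefficients is not normally distributed unless at least one path is estimated very precisely. Comparing it with normal critical values then rejects less often than the nominal level allows. This costs power where it matters most, when both paths are real but moderate. H4 is a listed hypothesis with its own power statement, and the mechanism is part of what Aim 2 sets out to explore. A null Sobel result could therefore be read as evidence against the theory when a better test on the same data would have supported it. The plan already recognises the non-normality, so the remaining gap is that it does not commit to a test that handles it.

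**Working it through.** **Why Sobel is conservative.** Write z_a = a/s_a and z_b = b/s_b for the two paths. The Sobel statistic is ab / √(a²s_b² + b²s_a²). Dividing top and bottom by s_a·s_b gives z_S = z_a·z_b / √(z_a² + z_b²), which is always smaller than the weaker of the two path statistics. If both equal z, then z_S = z/√2, so each path must exceed 1.96 × 1.414 = 2.77 before Sobel rejects. With both at 2.5, z_S = 6.25/√12.5 = 1.77: not significant, although each path is. If one path is very strong, z_S approaches the weaker z and the penalty fades.

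**Inputs.** From the plan: Sobel with a normal reference, alpha 0.05, N of 75 to 120, 60 per sequence, equations (2) to (4). Assumed, because the plan does not say: two-sided testing, and a numeric meaning for medium. One choice is 0.39 for each path (about √0.15 = 0.387). X is a two-arm contrast, so another is d=0.5 on that path, with b of 0.39, about 0.31 (r=0.3: 0.3/√(1 − 0.09) = 0.314) or 0.26. A 60:60 indicator has SD 0.5, so a standardised path of 0.39 corresponds to d = 0.39/0.5 = 0.78.

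**Method.** Equations (2) to (4) were simulated by ordinary least squares, one record per person, unit residual SD, 20,000 to 40,000 trials (8,000 for the Monte Carlo product interval).

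**The plan's own figure.** With both paths 0.39, two-sided Sobel power is 67% at n=75, 72% at 80, 77% at 85, 80% at 90 and 94% at 120. The claim of more than 80% reproduces at the planned 120 and from about 90 upward. At 75 it reproduces only one-sided (83.5%).

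**Sobel against the joint-significance or Monte Carlo test.**

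| Path sizes | n | Sobel | Alternative | Loss (points) |
|---|---|---|---|---|
| a=b=0.39 | 75 | 67% | 81% | 14 |
| a=b=0.39 | 120 | 94% | 97% | 3 |
| two-arm d=0.78, b=0.39 | 120 | 95% | 97% | about 3 |
| two-arm d=0.5, b=0.39 | 120 | 66% | 77% | 11 |
| two-arm d=0.5, b about 0.31 | 120 | 53% | 71% | 18 |
| two-arm d=0.5, b=0.26 | 120 | 40% | 61% | about 21 |

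The pattern follows from the formula. At n=120, b=0.39 gives an expected z_b of about 0.39 × √120 = 4.3, well beyond 2.77. By contrast, d=0.5 gives z_a of about 0.5 × √120/2 = 2.7 and b=0.26 gives z_b of about 2.8, where the penalty is close to its largest.

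**Percentile bootstrap** (1,000 trials of 1,000 resamples, n=120): 97% at a=b=0.39, and 61% at d=0.5 with b=0.26, in line with the other alternatives.

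**False-positive rate** with no TLC effect on satisfaction and b=0.39: Sobel about 1.6% (n=75) to 2.7% (n=120); joint-significance and Monte Carlo tests about 4.4% to 5.4%. When both paths are zero, all three are far below 5%. The percentile bootstrap's false-positive rate was not simulated.

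**The case against.** The strongest reply is that the cost is small where it counts. If medium means 0.39 on both paths, then at the planned 120 Sobel has 94% power, well above the plan's claim, and the better test adds only 3 points. This stands, and it rules out two readings that the upper figures invite. A reader might infer that the trial gives up 20 points of power whatever the effects are, or that the power claim fails at the planned size. The documents support neither, because they put no number on medium and the claim holds at 120 under 0.39. The same silence means that the 3-point figure cannot be taken as the plan's own. With a two-arm d=0.5 the loss is 11 to 21 points.

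Second, Sobel errs on the safe side, and H4 is a mechanism question in a Stage 1 pilot. This also stands and limits the consequence.

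Third, the simulation is simpler than the planned analysis. There are six assessments and an adjustment for earlier wellbeing, either of which could change the precision of both paths. That is a real limit on the percentages. It does not alter the algebra, by which Sobel falls below the weaker path statistic.

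Two further inferences should be resisted. A reader might say that a wrong symmetric confidence interval is planned, but the H4 text specifies a z test and no interval. A reader might also say that the team is free to pick among tests afterwards. The text commits to Sobel and treats the others as additional; what it lacks is a rule for disagreement.

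**Conclusion.** The point holds as a free improvement. The named H4 test is conservative and the better methods are optional. At n=120 the power cost is about 3 points if both paths are 0.39, and 11 to about 21 points if the two-arm effect is d=0.5 with b between 0.39 and 0.26. At n=75 with both paths 0.39 it is 14 points. These figures rest on two-sided 0.05, assumed path sizes and a single-level model; repeated measures and baseline adjustment could shift all of them. The consequence is a greater chance of missing a real mechanism. It does not produce false mediation claims, and the H1 efficacy test and the feasibility results are unaffected.

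**What to change.** In the H4 text, name one test of the indirect effect: a percentile bootstrap of the product a·b that resamples whole participants, with mediation concluded if the 95% interval excludes zero. Report the Sobel z as supportive only, and delete the sentence that leaves other tests for consideration.

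In Power and Sample Size, restate the mediation power for that test, giving the numeric size assumed for each path, how the two-arm exposure is scaled, and whether the test is one- or two-sided. Ideally base it on a simulation of the longitudinal, baseline-adjusted model, which would also confirm the bootstrap's false-positive rate.

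The cost is SAP wording and a little computing, with no additional participants, data or design change.
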